5.5 Study Evaluations

Providers:

Screening: During screening, we will determine whether potentially eligible providers meet the eligibility criteria for participation in the study by reviewing inclusion and exclusion criteria. The list of provider screening variables is included as part of the attached Provider Survey Instrument (Attachment R).

Demographic and Practice Characteristics Survey: Providers complete a brief demographic and practice characteristics survey prior to randomization. The list of demographic and practice characteristics variables is attached as part of the Provider Survey Instrument (Attachment R).

Aim 3 Qualitative Interview: After completion of patient enrollment, intervention arm providers who participate in the qualitative interview will be invited to do a 15-20 minute qualitative interview. During the interview, providers will be asked questions about their experience providing care to women receiving the MyPath intervention and facilitators and barriers to implementing MyPath in clinical practice (see attached interview guide, Attachment S).

Patients:

Screening: During screening, we will determine whether potentially eligible patients meet the eligibility criteria for participation in the study by reviewing inclusion and exclusion criteria. We will ask additional screening questions in service of obfuscating the specific purpose of the study until after patients have attended their medical appointment (as discussed above in section 5.3). All screening questions are detailed in the Patient Survey Instruments (Attachment Q).

Intervention: Intervention arm participants will be asked questions after their scheduled visit about whether they accessed and used the MyPath website prior to their visit. They will also be assigned a personal code at the start of the MyPath tool. We will then ask participants to provide the personal code at the post-visit survey so that we can obtain analytic information on their use of the tool after the fact. Analytics collected using this method will include the length of time the patient stayed on the MyPath webpage, which modules they used, and whether or not they navigated to the MyPath summary page. MyPath can be viewed at va.mypathool.org and the MyPath Intervention Overview (Attachment C) includes example screen shots from each main section of the web-based intervention.

Study Surveys (baseline, post-visit, 3 months, 6 months): Veterans in both the control and intervention arms will complete a demographic and health survey at baseline (at the time of enrollment), a post-visit survey, a 3-month survey, and a 6-month survey. The baseline, 3-month and 6-month surveys will be completed via telephone with a study RA utilizing VA REDCap for data collection.

The post-visit survey will primarily be completed online. Veterans will be sent a VA-approved Qualtrics one-way text message with a link to complete the post-visit survey online after their appointment. Veterans will receive no more than 5 additional brief Qualtrics one-way text messages within the three weeks following their primary care appointment to remind them to complete the post-visit survey. If the Veteran does not complete the post-visit survey online, RAs will reach out to the Veteran via telephone and utilize VA REDCap for the post-visit survey data collection.

- One-way text message that will be sent to Veterans to complete the post-visit survey online via Qualtrics:

It's time to complete your VA study survey:

[Link to Qualtrics Survey]

Thanks for contributing! Questions? Call [contact]

- Example reminder one-way text messages that will be sent to Veterans to complete the post-visit survey online via Qualtrics:

Reminder: It's time to do the next survey for the women Veterans study:

[Link to Qualtrics Survey]

Questions? Call 206-XXX-XXXX

Don't forget to complete the next VA study survey to receive \$50:

[Link to Qualtrics Survey]

Questions? Call 206-XXX-XXXX

Please complete this survey for "Improving Outcomes for Women Veterans":

[Link to Qualtrics Survey]

Questions? Call 206-XXX-XXXX

Reminder: It's time to do the next survey for the women Veterans study:

[Link to Qualtrics Survey]

Questions? Call 206-XXX-XXXX

Don't forget to complete the next VA study survey to receive \$50:

[Link to Qualtrics Survey]

Questions? Call 206-XXX-XXXX

Don't forget to complete your VA survey by MM/DD to receive \$50!

[Link to Qualtrics Survey]

Questions? Call 206-XXX-XXXX

Survey reminder! Your responses will help VA improve care for women Vets.

[Link to Qualtrics Survey]

Questions? Call 206-XXX-XXXX

Reminder from VA! Please complete this study survey (\$50 compensation)

[Link to Qualtrics Survey]

Questions? Call 206-XXX-XXXX


Please complete this survey for “Improving Outcomes for Women Veterans”:
 
[Link to Qualtrics Survey]
 
Questions? Call 206-XXX-XXXX

Reminder: Submit your next survey to help improve women Vets’ healthcare:
 
[Link to Qualtrics Survey]
 
Questions? Call 206-XXX-XXXX

Reminder: Submit survey to support women’s health at VA and receive \$50:
 
[Link to Qualtrics Survey]
 
Questions? Call 206-XXX-XXXX

Please complete VA women’s health study survey by MM/DD to receive \$50:
 
[Link to Qualtrics Survey]
 
Questions? Call 206-XXX-XXXX

Reminder: Help the VA improve care for women Vets and receive \$50:
 
[Link to Qualtrics Survey]
 
Questions? Call 206-XXX-XXXX

All survey questions assessed at each timepoint are provided in the attached Patient Survey Instruments (Attachment Q) and summarized below.

- Baseline survey: Demographics, pregnancy intentions, and whether the patient is at risk of unintended pregnancy (UIP) will be assessed. Baseline preconception health risks will be assessed.
- Post-visit survey: The primary outcome of the occurrence of a reproductive planning discussion with SDM and the secondary outcomes of communication self-efficacy and family planning knowledge will be assessed among all participants. Secondary outcomes relating to contraceptive choices and decisions will also be assessed post-visit among the subgroup at risk of UIP. Whether participants discussed preconception health risks or received any services related to preconception health risks identified at baseline will be assessed among participants considering pregnancy. At the end of the post-visit survey we will ask questions related to use of the intervention for Aim 3, including collecting the users’ assigned personal codes as described above.
- 3- and 6-month surveys: Changes in pregnancy goals and whether the patient continues to be at risk of UIP will be assessed. Secondary outcomes relating to contraceptive use and unintended pregnancy will be assessed among the group remaining at risk of UIP. Preconception health behaviors, an exploratory outcome, will be assessed.

Aim 3 Qualitative Interview: Intervention arm patients who participate in the qualitative interview will be asked questions about their experience receiving the MyPath text message, using or not using the MyPath intervention, and using any other similar health-related tools previously (see interview guide, Attachment S).

Clinic Leaders:

Brief Demographic Survey and Qualitative Interview: Clinic leaders who complete the qualitative interview will be asked questions about their experience having the MyPath intervention provided to patients in their clinic and facilitators and barriers to implementing MyPath in clinical practice. See attached interview guide (Attachment S).

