Patients: Enrolled patients will receive \$25 by electronic funds transfer from VA or receive a \$25 Amazon gift card after completing three of the study surveys (baseline, at 3 months, and at 6 months), and, when applicable, after completing a qualitative interview. Enrolled patients who complete the post-visit survey after their scheduled primary care appointment will receive \$50 by electronic funds transfer from VA or a \$50 Amazon gift card. This means that patients can receive up to \$125 for completing all study surveys for Aims 1 and 2, and an additional \$25 if invited to do a qualitative interview for Aim 3. Payments will be initiated after each completed study survey or interview; thus, patients will be paid for partial study participation. We will give Veterans the option of receiving a gift card or an electronic fund transfer from VA as payment for their study participation. VA electronic fund transfer payments are distributed through the VA Austin payment center. If a Veteran would like to receive their payment by electronic funds transfer and they have not previously filled out VA Form 10-091, Veterans have the option to complete a paper VA Form 10-091 (returned by mail) or complete VA Form 10-091 online through the VA's online Customer Engagement Portal. If a Veteran chooses to receive their payment as an Amazon gift card, these will be mailed by the study team or sent as a gift card claim code in an unencrypted email from the study email account. No Veteran identifiers would be included in the email (Attachment Z). Veterans may experience a delay in receiving electronic funds transfer payments for up to 6 months due to processing time.

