Because informative missingness would violate the covariate-dependent missing at random (CDMAR) assumption of the standard multiple imputation procedure, we will conduct sensitivity analyses in which we multiply impute missing data under plausible informative missing data mechanisms – in particular, lower contraceptive continuation rates among participants with missing values of this outcome, in one or both arms. In all analyses, we will check for departures from model assumptions.

Aims 1 and 2 - Outcome Analyses:

Intention to Treat: Primary analyses of treatment effects will be intent-to-treat, with participants analyzed in the groups to which they were originally assigned irrespective of whether or not they received the intervention. Therefore, participants who “cross-over” from their assigned study arm will be analyzed in their originally assigned group. Participants will be withdrawn/removed from the study and excluded from analysis after enrollment in either of these circumstances:

- Participants who do not attend their scheduled visit with the study provider after enrollment (and thus have an undefined outcome for patient-provider reproductive planning discussion).
- Participants who find out they are pregnant during their enrollment visit (and thus would have been ineligible had this been known prior to enrollment).

Secondary analysis will utilize causal inference methods (e.g., using instrumental variables) to estimate the treatment effect between participants who actually used the MyPath tool vs. those who did not (i.e., accounting for adherence).

Analytic Subgroups: Certain secondary outcomes will be analyzed only among a pre-defined cohort/subgroup of participants. Assignment to these groups is made at patient screening/enrollment (pre-intervention). Definitions of the full sample and analytic subgroups are as follows:

- **The full sample:** includes all individuals who are eligible for and enrolled in the study based on inclusion/exclusion criteria (capable of pregnancy with no prior history of hysterectomy, oophorectomy, sterilization, not currently pregnant, interested in receiving information about either pregnancy planning or birth control, and able to receive VA text messages).

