5.7 Withdrawal of Subjects

As discussed above in the Intention to Treat approach of section 5.6, we plan to withdraw participants from the study after enrollment under two circumstances. Both of these criteria will be assessed at the start of the post-visit survey and withdrawal would happen before assessment of any study outcome measures. The patient information statement (Attachment J) details the circumstances in which a patient could be withdrawn from the study. Participants will be removed from the study and excluded from analysis after enrollment in either of these circumstances:

- Participants who do not attend their scheduled visit with the study provider after enrollment (and thus have an undefined outcome for patient-provider reproductive planning discussion).
- Participants who find out they are pregnant during their enrollment visit (and thus would have been ineligible had this been known prior to enrollment).

Research participants may withdraw from the research at any time by notifying an RA or LSI. Participants may withdraw permission for the research team to access their medical record data by notifying an RA or LSI in writing. RAs and LSIs will notify the PI/SC, study manager, and research coordinator of any withdrawals. The PI/SC, study manager, research coordinator, or database manager will set the status of the participant to “Withdrawn/Do not contact” in the patient crosswalk, preventing further contact for study follow-up. There will be no consequences to the participant if they choose to withdraw from the research.

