to contact us with questions or to tell us they are not interested in the study: first, they may complete the Qualtrics survey (unique link embedded in the email) which asks them if they would like to be contacted by the study team by phone (or not); second, they may call the study manager at the number listed in the email.

Covariate and Outcome Variables:

We will pull data to describe the enrolled patient population, include in our analysis models (covariates) and compare reproductive health outcomes (preconception health and contraceptive use) between survey and medical record data. These CDW variables will be pulled for all enrolled patients (see Administrative Data Sources and Codes, Attachment D). The relevant reproductive health fields will not be identifiable or contain PHI; however, patient SSNs will be used to pull the CDW data for enrolled participants and link it to patient-reported data collected during the study. Once that matching is complete, SSNs will only be stored in the study crosswalk and not in the analytic datasets.

- Joint Legacy Viewer (JLV) for viewing medical record and confirming appointment status: For enrolled Veteran participants who are not reachable for the Post-Visit survey, study staff will review their medical record using the JLV application to confirm whether the Veteran attended or did not attend their appointment and if so, whether pregnancy was diagnosed at that visit. Veterans who did attend their appointment and have no pregnancy diagnosis documented at the visit will be included in analyses (with missing outcome values) per our intent-to-treat approach. Veterans who did not attend their appointment or who had a pregnancy diagnosed at their appointment will be withdrawn from the study and excluded from analyses (i.e., they are handled in the same way as Veterans reached for the post-visit survey).

In addition, for Veterans not-reachable for the Post-Visit survey, but who are included in analyses (because they did attend their visit and were not pregnant), study staff may use JLV to abstract details about the study-associated visit for analysis. These details include whether a discussion about reproductive health or any referrals or new prescriptions relating to reproductive health were documented as part of the visit. These data will be recorded using an abstraction form (Attachment

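### Attendance at the index visit decides who is analysed, yet it is unverified self-report for women who answer the post-visit survey and checked in the record only for women who do not

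*Combined protocol and SAP*

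**What the plan says.** All references are to the combined protocol and SAP.

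- **Who is excluded.** Section 5.6 (Intention to Treat) and section 5.7 remove two groups after enrolment. The first is "Participants who do not attend their scheduled visit with the study provider after enrollment", whose primary outcome the protocol regards as undefined. The second is women who learn at that visit that they are pregnant.
- **How this is established for responders.** Section 5.7: "Both of these criteria will be assessed at the start of the post-visit survey", before any outcome is measured. Section 5.5: "The post-visit survey will primarily be completed online", with a telephone call from a research assistant as the fallback. On timing, 5.5 says: "Veterans will be sent a VA-approved Qualtrics one-way text message with a link to complete the post-visit survey online after their appointment".
- **How it is established for the rest.** Section 7.0 (Joint Legacy Viewer item): "For enrolled Veteran participants who are not reachable for the Post-Visit survey, study staff will review their medical record using the JLV application". Staff look for attendance and for a pregnancy diagnosis at the visit. Those who attended and had no such diagnosis "will be included in analyses (with missing outcome values) per our intent-to-treat approach".
- **Payment.** Section 5.2: "Enrolled patients who complete the post-visit survey after their scheduled primary care appointment will receive" 50 dollars. The 3- and 6-month surveys pay 25 dollars each. Several of the sample reminder texts in 5.5 mention the 50 dollars.

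**The concern.** Both criteria are exclusions made after randomisation, so they fix the denominator of the primary analysis and of the secondary analyses that follow. Such exclusions are safest when they rest on evidence that is objective, collected in the same way for everyone, and blind to arm. Here the larger group (if most women respond, as the 5% attrition assumption implies) is classified by its own answer, usually with no interviewer present, and nothing in the text verifies that answer.

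A woman who did not attend but says that she did would supply a primary outcome for a visit that never took place, and could stay in the Aim 2 follow-up. If such women mostly report no discussion, the treatment difference is diluted. If they were more common in one arm, the difference would be shifted. The same split in evidence applies to pregnancy found at the visit.

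**Working it through.** **1. Do the documents verify responders anywhere?**

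| | Answers the survey | Not reached |
|---|---|---|
| Evidence of attendance and pregnancy | Own answer at the start of the survey (5.7), mostly online (5.5) | Chart review (7.0) |
| Record check stated | None | Yes |
| Did not attend | Withdrawn, excluded | Withdrawn, excluded |
| Attended, not pregnant | Outcome from survey | Kept, outcome missing |

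The post-appointment timing of the text in 5.5 does not imply that attendance was confirmed first. If it had been, the chart would not be needed later to learn whether non-responders attended.

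**2. The plan's own sample size.** Inputs from 5.6: 50% v 70%, two-sided 5%, 80% power, 30% non-use, coefficient 0.01, 15 patients per provider, 5% attrition. Section 5.1 gives 1:1 allocation.

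- Two proportions, pooled variance under the null: 93 per arm.
- Non-use: 93 / (1 − 0.30)² = 189.8.
- Design effect: 1 + (15 − 1) × 0.01 = 1.14.
- Attrition: 189.8 × 1.14 / 0.95 = 227.8, rounded up to 228 per arm, or **456** in total, as stated.

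The point made here does not alter that figure.

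**3. Scale of the problem.** With 30% non-use the expected intention-to-treat difference is 0.70 × 20 = 14 points (50% v 64%). Let q be the share of enrolled women who miss the visit and r the share of those who report attending. The documents give neither. I take q = 5–15% and r = 10–30%, equal in both arms, with every misreporter answering that no discussion took place. The 5% attrition is applied on top of no-shows.

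- Misreporters = 456qr; attenders = 456(1 − q).
- Contaminated share c = 456qr / [456(1 − q) + 456qr].
- Difference = 14(1 − c), from rates 50%(1 − c) and 64%(1 − c).
- Effective n per arm = (women analysed) × 0.95 / 1.14 / 2.
- Power = Φ{d / √([pC(1 − pC) + pT(1 − pT)] / n) − 1.96}.

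With all 456 women attending, n = 190 and power = Φ(0.14 / 0.0503 − 1.96) = 79.5%.

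| q, r | Misreporters | Attenders | c | Difference | Power, attenders only | Power with misreporters |
|---|---|---|---|---|---|---|
| 5%, 10% | 2.3 | 433.2 | 0.5% | 13.9 | 77.4% | 77.2% |
| 10%, 20% | 9.1 | 410.4 | 2.2% | 13.7 | 75.2% | 74.0% |
| 15%, 30% | 20.5 | 387.6 | 5.0% | 13.3 | 72.8% | 69.9% |

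The loss due to misreporting is therefore 0.2 to 2.9 points.

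**4. Unequal misreporting, for illustration only.** If non-attenders made up 5% of the analysed women in the intervention arm alone, the difference would be 64 × 0.95 − 50 = 10.8 points. If in the control arm alone, it would be 64 − 50 × 0.95 = 16.5 points. With no true effect, the imbalance alone would give 50 × 0.05 = 2.5 points. Nothing in the documents shows that misreporting would differ by arm.

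**The case against.** Much of the case on the other side stands.

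- **One rule, two sources.** A reader might infer that the analysis set has two conflicting definitions, or that the statement in 7.0 that both groups are handled alike is wrong. The documents do not support that. The criteria and their consequence agree across 5.6, 5.7 and 7.0, and falling back on the chart when self-report is unavailable is ordinary practice.
- **Payment.** A reader might infer that admitting non-attendance costs a woman 50 + 25 + 25 = 100 of the 125 dollars. That is inference. The documents pay for completing surveys, but do not say whether a woman withdrawn at the start of the post-visit survey is unpaid, or whether she knows what her answer entails. The gap in verification exists with or without an incentive.
- **Unseen attachments.** The attendance item and its branching are in the survey attachment, and the record variables in the administrative data attachment. Neither is available, so a check described only there cannot be ruled out.
- **Size.** Women enrol about a week before the visit and must plan to attend. The largest loss needs both extreme rates and every misreporter answering no. At that extreme, more power goes to no-shows whom the plan means to exclude (79.5% to 72.8%) than to misreporting (72.8% to 69.9%). Enrolment may also rise to 570.
- **Remedy.** Holding the survey text until the record shows a completed visit would delay a recall-based outcome. A pregnancy learned of at the visit may not be coded there. Chart review of everyone by the research assistants could reveal which provider each patient sees, which 5.1 (Blinding) is meant to prevent. These points limit the fix; they do not remove the need for it.

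**Conclusion.** The gap is real. A post-randomisation exclusion that decides membership of the primary analysis rests on unverified self-report for responders, while a record check is specified only for women not reached. Its likely effect is small: 0.5–5.0% of the analysed set, a 14-point difference reduced to 13.9–13.3 points, and at most about 3 points of power. Those figures depend on assumed no-show and misreporting rates, on misreporters reporting no discussion, and on equal rates in the two arms. The text supports neither a claim that the result is materially biased nor one that women are paid to say they attended. The change is worth making because it is cheap and puts a post-randomisation exclusion on objective evidence.

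**What to change.** In 5.6 and 5.7, state that:

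- the status of the index appointment with the study provider will be verified from the CDW/VSSC record for every enrolled woman, whether or not she answers the survey;
- the data requisitioner will make this pull blind to arm, and the research assistants will take no part in it;
- attendance for the primary analysis set is defined by that record, the survey answer is kept as a cross-check, and disagreements are reported by arm;
- for pregnancy found at the visit, the record supplements the self-report and does not replace it.

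The survey text should go out as now, without delay. Because confirming the study provider reveals who that provider is, the requisitioner should not hold the provider allocation list.

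The cost is a small extra data pull and the resolution of a few discrepancies. CDW variables are already drawn for all enrolled patients (7.0), and appointment lists are already pulled weekly during recruitment (5.2).

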5.6 Data Analysis

Aims 1 and 2 - Sample Size:

Sample size and power calculations are based on our primary outcome, occurrence of reproductive planning discussion between patient and provider with shared decision making (SDM), and rely on formulas specified for use in cluster randomized trials accounting for non-use of the tool in the intervention group and attrition.[39] We estimate that the baseline prevalence of discussions of contraception and/or preconception health among women who could potentially become pregnant will be 50%, based on estimates from the nationally-representative VA ECUUN study and our pilot study.[2] Based on field testing, we estimate that 30% of women participants enrolled in the intervention arm who receive the text with the MyPath link will not actually view the tool and the sample size calculation will thus account for this estimated non-use. Assuming a kappa coefficient of 0.01 and attrition of 5%, a sample of 456 patients (approximately 15 patients for each of 30 providers) will yield 80% power in 2-sided tests with a type-1 error rate of 5% to detect a 20-percentage point increase in reproductive planning with SDM to 70%. This difference is clinically meaningful and consistent with what we observed in our pilot (22% increase).

Aims 1 and 2 - Missing data and subject dropouts:

For the 3- and 6-month follow-up periods, we assume 20% attrition (15% lost to follow up and 5% who either become pregnant or change to desiring pregnancy). This is a conservative estimate based on 7% attrition at 3-months in our pilot. All appropriate efforts will be made to avoid missing data, including monitoring of missingness and subject dropout rates by the PI and study manager or research coordinator biweekly during the study data collection phase. The research coordinator will investigate causes and remedies. For key analysis variables that have 15% or more missing values, we will analyze factors that are associated with having a missing value and perform a sensitivity analysis using multiple imputation to allow an unbiased analysis for all subjects.

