- **At risk of unintended pregnancy (UIP):** a subgroup of the full sample defined as having had sex with a man in the past 12 months who has not had a vasectomy and not currently seeking pregnancy. Outcomes related to contraception will be assessed in the subgroup at risk for UIP.
- **Considering pregnancy:** a subgroup of the full sample who are considering or ambivalent about pregnancy in the next few years. The exploratory preconception health behaviors outcomes will be assessed in this subgroup.

Description of the study populations: Provider, patient, and clinic leader participants will be described through summary statistics of demographic characteristics, and for providers, practice characteristics.

Aim 1 Primary Outcome: The analysis for our primary outcome of patient-provider discussion of reproductive planning with share decision making (SDM) will be assessed post-visit in **the full sample**. For our Aim 1 primary outcome analysis, we will use a mixed effects logistic regression model to test whether the odds of occurrence of reproductive planning with SDM is significantly different in the intervention versus control arm post-visit. In addition to estimating the odds ratio, we will also estimate the difference in predicted probabilities between the intervention and control group.

Covariates to be included in adjustment models are as follows:

- Study site (categorical)
- Clinic practice-type (binary) – Women’s Clinic Y/N
- Visit Type (virtual/telephone vs. in-person)
- Patient Age (categorical)
- Patient Race/ethnicity (categorical)
- Patient Household Income (categorical)
- Patient Marital Status (categorical)
- Patient Parity (categorical)
- Mental Health Diagnosis (one or more, binary)
- Medical Comorbidity (one or more, binary)

Aim 1 Secondary Outcomes: Secondary outcomes for Aim 1 will be assessed post-visit.

Secondary outcomes assessed **in the full sample** include provider-patient communication self-efficacy and reproductive planning knowledge. Secondary outcomes assessed **in the subgroup at risk of UIP** include contraceptive decisional conflict, values concordance, and contraceptive method decision. We will use a mixed effects logistic regression model to test whether these outcomes are different in the intervention versus control arm post-visit.

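### Section 5.5 assesses the 3- and 6-month outcomes in women still at risk of unintended pregnancy (UIP), whereas section 5.6 uses a subgroup fixed before the intervention

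*Combined protocol and SAP*

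**What the plan says.** In section 5.5, the bullet on the 3- and 6-month surveys begins: "Changes in pregnancy goals and whether the patient continues to be at risk of UIP will be assessed". It continues: "Secondary outcomes relating to contraceptive use and unintended pregnancy will be assessed among the group remaining at risk of UIP". The post-visit bullet just above it has no such condition: "Secondary outcomes relating to contraceptive choices and decisions will also be assessed post-visit among the subgroup at risk of UIP".

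Section 5.6 (Analytic Subgroups) says of the subgroups: "Assignment to these groups is made at patient screening/enrollment (pre-intervention"). The at-risk subgroup is defined as "having had sex with a man in the past 12 months who has not had a vasectomy and not currently seeking pregnancy". Under Aim 2 Secondary Outcomes, continuous use, consistent use and unintended pregnancy at 3 and 6 months are assigned to the subgroup at risk, with no requirement that a woman still be at risk. The exploratory goals-concordant measures in the same section accept that members of this subgroup may come to want a pregnancy, and they score contraceptive use in women who want one at that time.

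The missing-data paragraph of section 5.6 points the other way. For the 3- and 6-month follow-up, "we assume 20% attrition (15% lost to follow up and 5% who either become pregnant or change to desiring pregnancy"). The governing principle is also in section 5.6: "Primary analyses of treatment effects will be intent-to-treat, with participants analyzed in the groups to which they were originally assigned".

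Section 5.7 withdraws enrolled women in only two planned circumstances: a missed study visit, or a pregnancy discovered at that visit. A later pregnancy or a change of goals is not among them.

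**The concern.** Two populations are described for the same secondary outcomes. One is fixed before the intervention. The other depends on what has happened to the woman by 3 or 6 months.

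The Abstract lists among MyPath's objectives helping women consider their reproductive goals and fit decisions about contraception and the timing of pregnancy to them. Whether a woman is still at risk at follow-up may therefore depend on the arm. Restricting the comparison to women still at risk would give up the protection of randomisation for the Aim 2 contrasts. If becoming pregnant is taken to end at-risk status, the restriction could also remove events from the unintended-pregnancy outcome. If the attrition label were carried into the analysis, women whose status is known would be handled as missing.

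**Working it through.** **Step 1: the passages side by side.**

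| Place | Population for the 3- and 6-month outcomes |
|---|---|
| 5.5, 3- and 6-month surveys | Women still at risk after re-assessment |
| 5.6, Analytic Subgroups | Membership set before the intervention |
| 5.6, Aim 2 Secondary Outcomes | The at-risk subgroup, no later condition |
| 5.6, goals-concordant measures (exploratory) | The at-risk subgroup, including women who now want pregnancy |
| 5.6, missing data | Pregnancy and changed desire labelled attrition |
| 5.7 | No withdrawal for later pregnancy or changed goals |

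A woman who now wants pregnancy would fail the section 5.6 definition if it were applied again at follow-up. The exploratory measures can include her only if membership is fixed at enrollment. For the Aim 2 secondary outcomes themselves, keeping her follows from the pre-intervention assignment rule and is not stated separately.

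**Step 2: does the plan's sample size depend on this?** Inputs from section 5.6: 50% versus 70%, two-sided 5%, 80% power, 30% non-use, coefficient 0.01, cluster size 15, attrition 5%.

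- Two proportions, no clustering: 93 per arm.
- Non-use: 93 / (1 − 0.30)² = 93 / 0.49 = 189.8.
- Clustering: design effect 1 + (15 − 1) × 0.01 = 1.14; 189.8 × 1.14 = 216.4.
- Attrition: 216.4 / 0.95 = 227.8, rounded up to 228 per arm, 456 in total.

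The plan's figure is reproduced exactly. It rests on the post-visit outcome in the full sample with 5% attrition. The 20% follow-up figure does not enter it.

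**Step 3: how many women, on the plan's own allowance?** The 20% is 15% + 5%, so the 5% is a quarter of it. The fixed subgroup would retain 85% of at-risk women and the group still at risk 80%. The documents do not give the share of enrolled women who are at risk, so 60% to 100% is assumed here.

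- All 456 at risk: 387.6 versus 364.8, a gap of 0.05 × 456 = 22.8.
- 60% at risk (273.6 women): 232.6 versus 218.9, a gap of 13.7.
- All of the 570 maximum at risk: a gap of 0.05 × 570 = 28.5.

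**Step 4: can the bias be sized?** In one arm let p be use in the fixed subgroup, d the fraction who leave, and u use among leavers. Use among those remaining is (p − d·u) / (1 − d). The documents give none of these by arm. Purely as an illustration, assume p = 60% in both arms (no effect) and u = 0:

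| Leaving: control / intervention | Use among those remaining | Spurious difference |
|---|---|---|
| 5% / 5% | 63.2% / 63.2% | 0 |
| 3% / 7% | 61.9% / 64.5% | 2.7 points |
| 5% / 10% | 63.2% / 66.7% | 3.5 points |
| 2% / 8% | 61.2% / 65.2% | 4.0 points |

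Reversing the arms reverses the sign. Neither size nor direction follows from the documents.

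**The case against.** The strongest reply is that the analysis population is already settled. Section 5.6 is the analysis section, and it fixes the subgroup and assigns the Aim 2 outcomes to it. Section 5.5 only summarises survey content whose detail is in Attachment Q. An analyst working from section 5.6 would use the fixed subgroup, and the exploratory measures suggest that women whose goals change are still asked about contraception.

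Much of this stands: most of section 5.6 supports the fixed subgroup, and nothing shows that the other one would be used. It does not remove the conflict. Both sections speak of assessing the outcomes in a group, and the missing-data paragraph of section 5.6 leans towards section 5.5. If the sentence is only survey routing, women no longer at risk may not be asked. Their outcomes would then be missing for the fixed subgroup and for the goals-concordant measures. Attachment Q is not among the documents, so this cannot be checked.

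Four stronger readings are tempting, and the documents do not support them.

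- *About 23 women is the most that could be affected.* The 5% is a planning assumption and covers only pregnancy and changed desire. Under the definition a woman can also leave through a partner's vasectomy or a year without sex with a man.
- *The attrition label decides whether the imputation sensitivity analysis is run.* The trigger reads "For key analysis variables that have 15% or more missing values", which concerns values actually missing. A recorded outcome is not missing, and no passage says to delete it.
- *The 5% can be added to the pilot's 7%.* The plan calls the 7% attrition without saying that it excludes pregnancy or changed goals, so the sum may double count.
- *Unintended pregnancies are excluded from their own outcome.* The Introduction defines such a pregnancy as unwanted or too early. A woman who has one was not seeking it and need not be read as having left the group.

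**Conclusion.** The inconsistency is in the current text and should be resolved before the Aim 2 analysis. Section 5.5 conditions the 3- and 6-month contraceptive-use and unintended-pregnancy outcomes on status at follow-up; the subgroup and Aim 2 paragraphs of section 5.6 do not. If section 5.5 were followed, these comparisons would depart from the intent-to-treat principle, and on one reading would lose pregnancies.

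The consequence is conditional and unquantified. The 5% allowance gives an order of magnitude of 14 to 23 women at N = 456, under the assumed at-risk share of 60% to 100%. The plan does not split the 5% between pregnancy and changed goals, so the number of unintended pregnancies at stake cannot be derived and may be zero. Bias is zero if leaving is balanced and use among the rest is equal. That MyPath shifts at-risk status is plausible from its stated aims but is not documented. The concern is confined to Aim 2 secondary outcomes; the primary outcome and the 456 are untouched.

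**What to change.** 1. In section 5.5, replace the group still at risk at follow-up with the at-risk subgroup fixed at screening/enrollment. Collect Aim 2 outcomes at 3 and 6 months from all its members, and analyse all those with available data.
2. In the missing-data paragraph of section 5.6, state that women of known status whose goals change, or who become pregnant after the enrollment visit, are not missing. Classify those pregnancies by intendedness as potential outcome events. Keep the existing exclusion in sections 5.6 and 5.7 for a pregnancy found at the enrollment visit.
3. Report any analysis limited to women still at risk as supportive only.
4. Check Attachment Q. If completed surveys skipped these women, report those outcomes as missing and handle them under the imputation and informative-missingness analyses already in section 5.6.

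The cost is wording in two places. Both arms are already surveyed by telephone at 3 and 6 months, and the goals-concordant measures already need contraceptive data from women who want pregnancy. No extra contacts or patients are required, and no stated sample-size calculation has to be redone. Answers already skipped may not be recoverable.
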